11.11. Solicited symptoms

The analysis of solicited symptoms will be performed in the safety and immunogenicity sub-cohort.

The number and percentage of subjects reporting each individual solicited local (any, grade ≥ 2 , grade 3) and general (any, related to vaccination, grade ≥ 2 , grade 3, grade ≥ 2 related to vaccination and grade 3 related to vaccination) AE during the solicited follow-up period will be tabulated by treatment group with exact 95% CI.

The number and percentage of doses followed by each individual solicited local (any, grade ≥ 2 and grade 3) and general (any, related to vaccination, grade ≥ 2 , grade 3, grade ≥ 2 related to vaccination and grade 3 related to vaccination) AE will be tabulated by treatment group, overall vaccination course, with exact 95% CI.

The percentage of doses followed by each individual solicited local and general (any, grade 3) AE will be presented in a bar chart by treatment group, overall vaccination course (2 doses combined), with exact 95% CI.

Occurrence of fever will also be reported per 0.5°C cumulative increments.

The number of days with a solicited symptom during the solicited follow-up period will also be presented by treatment group. The same tabulations will be done for grade 3 AEs and for general AEs with relationship to vaccination.

The number of days with a solicited symptom during the solicited follow-up period and beyond will also be presented by treatment group. The same tabulations will be done for grade 3 AEs and for general AEs with relationship to vaccination.

The number of solicited local and general symptoms ongoing beyond the 7-day post-vaccination period is given by treatment group as well as descriptive statistics (Q1, median, Q3) concerning the time-to-resolution (in days from the last day of the follow-up period to the last day the symptom was observed).

11.12. Large swelling reaction

In case a subject had a large swelling reaction after dose 1, the dose 2 should not be given to this subject. Therefore the summary is not per dose, but overall per subject whether the report of large swelling is after dose 1 or dose 2.

To check this per-protocol requirement, we will produce a list of subjects having reported large swelling reaction after dose 1, and received dose 2 nevertheless.

The number and percentage of subjects who experienced a large swelling reaction during the 30-day post-dose-1 vaccination period will be tabulated by treatment group with two-sided exact 95% CI.

The number and percentage of subjects who experienced a large swelling reaction during the 30-day post-dose-2 vaccination period will be tabulated by treatment group with two-sided exact 95% CI.

The number and percentage of subjects reporting large swelling reaction during the 30-day post vaccination period will be tabulated by treatment group with two-sided exact 95% CI.

The duration (=AE end date- AE start date+1) and the size of the large swelling reaction will be summarised by descriptive statistics such as mean, standard deviation, and minimum, Q1, median, Q3 and maximum values.

The presence of a large swelling reaction in a subject indicates with a high probability that the subject comes from the TB vaccine group but we will not eliminate any of these subjects from none of the ATP cohort (for efficacy, immunogenicity and safety).

11.13. Unsolicited symptoms

The proportion of subjects/doses with at least one report of unsolicited AE classified by the Medical Dictionary for Regulatory Activities (MedDRA) reported during the 30-day follow-up period (Days 0 to 29) will be tabulated with exact 95% CI by treatment group.

The same tabulations will be done for grade 3 AEs, AEs related to vaccination, grade 3 events related to vaccination and AEs resulting in a medically attended visit.

As only the subjects part of the safety and immunogenicity sub-cohort have a diary card to collect the solicited AEs, those symptoms (redness, swelling, pain at injection site, fever, headache, respiratory symptoms, malaise, myalgia)) reported for the other subjects were recorded in the Case Report Form (CRF) section on unsolicited symptoms.

Therefore to assess the impact of this situation, the following analyses will be proposed:

- The same analysis will be produced for the subjects with diary cards (part of the safety and immunogenicity sub-cohort).
- The proportion of subjects/doses with at least one report of unsolicited AE classified by MedDRA reported during the 7-day follow-up period (Days 0 to 7) will be tabulated with exact 95% CI by treatment group. Idem for grade 3 AEs, AEs related to vaccination, grade 3 events related to vaccination.
- The proportion of subjects/doses with at least one report of unsolicited AE classified by MedDRA reported after the 7-day follow-up period (Days 7 to 29) will be tabulated with exact 95% CI by treatment group. Idem for grade 3 AEs, AEs related to vaccination, grade 3 events related to vaccination.

The proportion of subjects with at least one report of unsolicited AE associated to the respiratory system classified by the MedDRA reported during the 90-day post-vaccination follow-up period (on or after Day 0 to Day 89) will be tabulated with exact 95% CI by treatment group, for all subjects in the TVC population.

The same tabulation will be done for, grade 2 or 3 AE associated to the respiratory system, grade 3 AE associated to the respiratory system, AE associated to the respiratory system related to vaccination, grade 2 or 3 AE associated to the respiratory system related to vaccination and grade 3 AE associated to the respiratory system related to vaccination.

The proportion of subjects with at least one report of grade 3 unsolicited AE associated to the respiratory system classified by the MedDRA reported during the 30-day post-vaccination follow-up period (on or after Day 0 to Day 29) will be tabulated with exact 95% CI by treatment group, for all subjects in the TVC population

Note that the list of preferred terms (PTs) “associated to the respiratory system” is actually the list of PTs which map to the MedDRA System Organ Class (SOC) of “Respiratory, thoracic or mediastinal conditions” regardless if this is their primary SOC or not.

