11.2. Secondary endpoints

Efficacy

- Incident cases of **Definite Xpert MTB/Rif positive Pulmonary TB disease** not associated with HIV-infection, meeting the second case definition.
Over a period starting 1 month post-dose 2 and lasting up to 35 months post last vaccination.
- Incident cases of **Definite Pulmonary TB disease** meeting the third case definition.
Over a period starting 1 month post-dose 2 and lasting up to 35 months post last vaccination.
- Incident cases of **Microbiological Pulmonary TB disease** meeting the fourth case definition.
Over a period starting 1 month post-dose 2 and lasting up to 35 months post last vaccination
- Incident cases of **Clinical TB disease** meeting the fifth case definition.
Over a period starting 1 month post-dose 2 and lasting up to 35 months post last vaccination

Refer to section 4 for case definitions.

Safety

- Occurrence of SAEs.
During the entire study period
- Occurrence of unsolicited AEs.
During the 30 day follow-up period following vaccination (day of vaccination and 29 subsequent days after each vaccine dose)
- Occurrence of solicited local and general AEs in the safety and immune sub-cohort.
During the 7 day follow-up period following vaccination (day of vaccination and 6 subsequent days after each vaccine dose).

- Occurrence of all pIMDs.
Over a period starting at Day 0 until 6 months post-dose 2.
- Occurrence of grade ≥ 2 haematological and biochemical, ***in the safety and immune sub-cohort***, levels at:
Days 0, 7, 30 and 37
(Amended: 29 January 2014)

Immunogenicity

- Evaluation of CMI responses with respect to components of the study vaccine, in the safety and immune sub-cohort:
 - ***Determined by the frequency of M72-specific CD4+/CD8+ T-cells per million cells identified after in vitro stimulation, as expressing any combination of immune markers among CD40L, IL-2, IFN- γ and TNF- α .*** (Amended: 29 January 2014)

Timepoints: prior to dose 1 (Day 0) and post-dose 2 (Day 60, Years 1, 2 and 3)
- Evaluation of humoral immune responses with respect to components of the study vaccine, in the safety and immune sub-cohort:
 - Determined by M72-specific antibody titres as measured by ELISA.
 - Determined by seropositivity rates as measured by ELISA.

Timepoints: prior to dose 1 (Day 0) and post-dose 2 (Day 60, Years 1, 2 and 3).

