4.2. Secondary endpoints

Efficacy:

- Incident cases of **Definite Xpert MTB/Rif positive Pulmonary TB disease** not associated with HIV-infection, meeting the second case definition.
Over a period starting 1 month post dose 2 and lasting up to 35 months post last vaccination.
- Incident cases of **Definite Pulmonary TB disease** meeting the third case definition.
Over a period starting 1 month post dose 2 and lasting up to 35 months post last vaccination.
- Incident cases of **Microbiological Pulmonary TB disease** meeting the fourth case definition.
Over a period starting 1 month post dose 2 and lasting up to 35 months post last vaccination
- Incident cases of **Clinical TB disease** meeting the fifth case definition.
Over a period starting 1 month post dose 2 and lasting up to 35 months post last vaccination

Refer to Section 5 for case definitions.

Safety:

- Occurrence of serious adverse events (SAEs).
During the entire study period
- Occurrence of unsolicited adverse events (AEs).
During the 30-day follow-up period following vaccination (day of vaccination and 29 subsequent days after each vaccine dose)
- Occurrence of solicited local and general AEs in the safety and immunogenicity sub-cohort.
During the 7-day follow-up period following vaccination (day of vaccination and 6 subsequent days after each vaccine dose)
- Occurrence of all Potential Immune Mediated Diseases (pIMDs).
Over a period starting at Day 0 until 6 months post-dose 2.
- Occurrence of grade ≥ 2 haematological and biochemical levels, in the safety and immunogenicity sub-cohort, at:
Days 0, 7, 30 and 37.

Immunogenicity:

- Evaluation of cell-mediated immune (CMI) responses with respect to components of the study vaccine, in the safety and immunogenicity sub-cohort:
 - Determined by the frequency of M72-specific CD4+/CD8+ T-cells per million cells identified after *in vitro* stimulation, as expressing any combination of immune markers among Cluster of Differentiation-40 Ligand (CD40L), interleukin-2 (IL-2), interferon-gamma (IFN- γ) and Tumour Necrosis Factor-alpha (TNF- α)

Timepoints: prior to dose 1 (Day 0) and post dose 2 (Day 60, Years 1, 2 and 3)

- Evaluation of humoral immune responses with respect to components of the study vaccine, in the safety and immunogenicity sub-cohort:
 - Determined by M72-specific antibody titres as measured by ELISA.
 - Determined by seropositivity rates as measured by ELISA.

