11.10.4. All symptoms

This analysis will be performed in the safety and immunogenicity sub-cohort.

- The percentage of subjects with at least one local AE (solicited and/or unsolicited), with at least one general AE (solicited and/or unsolicited) and with any AE during the solicited follow-up period (Day 0 to Day 6) will be tabulated by treatment group with exact 95% CI after each vaccine injection and overall.
- The percentage of doses followed by at least one local AE (solicited and/or unsolicited), by at least one general AE (solicited and/or unsolicited) and by any AE will be tabulated by treatment group, overall vaccination course, with exact 95% CI.

The same tabulations will be done for grade 3 AEs and for AEs causally related to vaccination.

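### SAP 11.13 puts Day 7 in both the early and the late unsolicited AE tables, and the early window is a day longer than the Day 0 to 6 solicited period

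*SAP*

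**What the plan says.** SAP section 11.13 first tabulates unsolicited AEs "reported during the 30-day follow-up period (Days 0 to 29"). It then explains that only subjects in the safety and immunogenicity sub-cohort have a diary card for solicited symptoms. In everyone else, the same kinds of symptom (injection-site reactions, fever, headache and so on) went into the unsolicited section of the case report form.

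To gauge the effect of this, the SAP adds three analyses:

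- the same analysis restricted to subjects with diary cards;
- a table of unsolicited AEs "reported during the 7-day follow-up period (Days 0 to 7");
- a table of unsolicited AEs "reported after the 7-day follow-up period (Days 7 to 29").

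The last two are each repeated for grade 3, related, and grade 3 related events.

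Other sections define the 7-day period differently. SAP section 11.10.4 tabulates all symptoms in the sub-cohort "during the solicited follow-up period (Day 0 to Day 6"). SAP section 4.2 defines the solicited endpoint as "During the 7-day follow-up period following vaccination (day of vaccination and 6 subsequent days after each vaccine dose"), and protocol section 11.2 gives the same definition. Protocol Table 23 marks 7 days after the first dose as Day 6 and 30 days after it as Day 29.

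**The concern.** The two split tables describe periods that should be complementary, one during and one after the same interval. As written, an AE on Day 7 falls in both.

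The early window also does not match the solicited period, and Day 7 is where that matters. Under the protocol glossary, a solicited-type symptom that starts outside the solicited period is reported as an unsolicited AE. In the sub-cohort, a headache starting on Day 6 is therefore a solicited event and one starting on Day 7 is unsolicited. Up to Day 6 the recording route differs between sub-cohort and other subjects; from Day 7 it is the same for both. A Days 0 to 7 table mixes the two situations, although the split was added to look at the consequences of that difference.

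Three things are at stake: single events appearing in two tables, an early table that reaches past the solicited window, and a mismatch with the sub-cohort's own Day 0 to 6 table if the two are read together.

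**Working it through.** **Inputs**

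| Window | Source | Stated label |
|---|---|---|
| Days 0 to 7 | SAP 11.13, early table | 7-day |
| Days 7 to 29 | SAP 11.13, late table | after the 7-day period |
| Days 0 to 29 | SAP 11.13, overall table | 30-day |
| Days 0 to 89 | SAP 11.13, respiratory AEs | 90-day |
| Days 0 to 6 | SAP 11.10.4; SAP 4.2; protocol 11.2 and Table 23 | solicited, 7-day |

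**Step 1: which counting convention does the SAP use?** Counting both end days, length = last day − first day + 1.

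- Days 0 to 29: 29 − 0 + 1 = 30, which matches its label.
- Days 0 to 89 ("90-day post-vaccination follow-up period (on or after Day 0 to Day 89")): 89 − 0 + 1 = 90, which matches.
- Days 0 to 6: 6 − 0 + 1 = 7, which matches.
- Days 0 to 7: 7 − 0 + 1 = 8, which does not match its 7-day label.

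**Step 2: could another convention rescue the text?** If the last day is excluded, length = last day − first day. Days 0 to 7 then has 7 days, but Days 0 to 29 has 29, Days 0 to 89 has 89 and Days 0 to 6 has 6. That repairs one label and breaks the other three.

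**Step 3: do the two split windows partition the 30 days?**

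- Early window: 8 days.
- Late window: 29 − 7 + 1 = 23 days.
- Sum: 8 + 23 = 31, against 30.
- Together they cover Days 0 to 29 completely; the only shared day is Day 7.

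**Step 4: does the early window match the solicited period?** Days 0 to 7 exceeds Days 0 to 6 by Day 7 alone. The excess in length is (8 − 7)/7 = 1/7 = 14%.

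**Step 5: after correction.** Days 0 to 6 and Days 7 to 29 give 7 + 23 = 30 days with no overlap. Their union is Days 0 to 29, and the early window equals the solicited period. The late window was already right, so only one limit is wrong.

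**The case against.** Nobody would dispute the slip itself. The case for leaving it alone is that little follows from it.

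- **No statistic adds the tables together.** Each reports subjects or doses with at least one event, and a subject with AEs on Day 2 and Day 15 would rightly appear in both even with disjoint windows. This is true. The defect is narrower: one and the same Day 7 event enters both tables.
- **The 14% is a ratio of window lengths.** It carries over to event counts only for background AEs spread evenly over time, and vaccine reactions may well cluster early. A proportion with at least one AE also need not rise in step with window length. This stands: 14% is not a forecast of inflation in any reported percentage.
- **No direct comparison with the solicited tables is planned.** The only sub-cohort comparison spelled out in section 11.13 repeats the same analysis in subjects with diary cards. That also stands, so the link to the solicited period is an inference. It is a strong one, because the two share the 7-day label and the recording of solicited symptoms is the stated reason for the split. The sub-cohort's all-symptoms table does run over Days 0 to 6.
- **The intended window can be guessed.** The 7-day label and the late table both point to Days 0 to 6, and the separate table and figures list may already have it right. That list is not available here. A programmer working from the SAP still has to choose between following the stated limits and departing from them silently.
- **Nothing inferential depends on it.** SAP section 13.3 treats these analyses as descriptive. This limits the importance of the point but does not remove the error.

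**Conclusion.** The point holds. As written, the early table covers eight days rather than seven, overlaps the late table on Day 7, and extends one day beyond the solicited period used everywhere else. SAP section 14, which lists changes from the planned analyses, does not redefine the 7-day period, so there is no sign that an eight-day window was intended.

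The size is one day: 31 day-slots for a 30-day period, and an early window 14% too long. How many subjects or doses this affects cannot be worked out from the documents, because they give no day-by-day AE rates. The grade 3, related, and grade 3 related versions of the two tables inherit the same overlap. The Days 0 to 29 table, the efficacy analyses, the success criteria and the type I error do not change.

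The conclusion rests on inclusive day counting, which the SAP's own 30-day, 90-day and Day 0 to 6 windows establish. That the early table was meant to cover the solicited period is an inference, but the overlap on Day 7 does not depend on it.

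**What to change.** In SAP section 11.13, change the early table's window from Days 0 to 7 to Days 0 to 6. Keep Days 7 to 29 for the late table. Apply the same limits to the grade 3, related, and grade 3 related versions, and check that the table and figures list uses them.

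The cost is one digit in the SAP and one programming parameter. No objective, cohort, endpoint or success criterion is affected.

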Note: Any change that falls under the definition of a protocol amendment (e.g. a change that affects the safety of subjects, scope of the investigation, study design, or scientific integrity of the study) MUST be prepared as an amendment to the protocol.

Randomisation:

Process of random attribution of treatment to subjects in order to reduce bias of selection.

Self-contained study:	Study with objectives not linked to the data of another study.
Site Monitor:	An individual assigned by the sponsor who is responsible for assuring proper conduct of clinical studies at one or more investigational sites.
Solicited adverse event:	AEs to be recorded as endpoints in the clinical study. The presence/occurrence/intensity of these events is actively solicited from the subject or an observer during a specified post-vaccination follow-up period.
Sub-cohort:	A group of subjects for whom specific study procedures are planned as compared to other subjects.
Subject:	Term used throughout the protocol to denote an individual who has been contacted in order to participate or participates in the clinical study, either as a recipient of the vaccine(s)/product(s) or as a control.
Subject number:	A unique number identifying a subject, assigned to each subject consenting to participate in the study.
“The Collaboration”:	Refers to the joint collaboration between GSK Biologicals and Aeras. GSK will act as the sponsor of this study whereas Aeras will provide financial and operational support.
Treatment:	Term used throughout the clinical study to denote a set of investigational product(s) or marketed product(s) or placebo intended to be administered to a subject, identified by a unique number, according to the study randomisation or treatment allocation.
Treatment number:	A number identifying a treatment to a subject, according to the study randomisation or treatment allocation.
Unsolicited adverse event:	Any AE reported in addition to those solicited during the clinical study. Also any ‘solicited’ symptom with onset outside the specified period of follow-up for solicited symptoms will be reported as an unsolicited AE.
Xpert MTB/RIF:	The Xpert MTB/RIF is a Nucleic Acid Amplification Test to detect Mtb complex and resistance to rifampicin in sputum samples using the GeneXpert® technology from Cepheid.

TRADEMARKS

The following trademarks are used in the present protocol.

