6.4.5.4. Rules for vaccination (Amended: 29 January 2014)**At individual subject level**

- *No second dose should be administered in a given subject who experiences Grade 3 redness and swelling, i.e. $\geq 100\text{mm}$, post dose 1 or Grade 2 or 3 respiratory AE post dose 1.*
- *No second dose should be administered in a given subject who develops TB disease after dose 1.*

At study level

- *An ad hoc IDMC review will be called if 2 or more subjects experience related Grade 2 or higher respiratory AEs within 90 days after any dose.*
- *Further enrolment and vaccination will be suspended if within 90 days after any study vaccine dose any of the following events are observed:*
 - *Related respiratory AE with Fatal outcome*
 - *Two or more subjects experiencing Grade 3 related Respiratory AE*
- *An ad hoc IDMC meeting will be called urgently for review. Vaccination may only be allowed to resume pending final VSMB approval.*

Table 6 Safety holding rules for vaccination (Amended: 29 January 2014)

Event	Grade	Occurrences	Action for subject(s)	Trial actions
Redness/Swelling at injection site (within 30 days after dose 1)	Grade 3 (>100mm)	any subject(s)	No dose 2 in same subject(s), keep in efficacy follow-up	-
TB disease (after dose 1)	n/a	Any subject(s)	No dose 2 in same subject(s), keep in efficacy follow-up	-
Respiratory SOC AE (within 90 days after dose 1)	Grade ≥ 2	1 subject	No dose 2 in same subject(s), but keep in efficacy follow-up	-
Respiratory SOC AE (within 90 days after dose 1)	Grade ≥ 2 related	≥ 2 subjects	Clinical assessment & further investigation at investigator discretion	Ad hoc IDMC review
Respiratory SOC SAE	Related & Fatal	≥ 1 subject		
Respiratory SOC AE (within 90 days after dose 1)	Grade ≥ 3, related	≥ 2 subjects	No dose 2 in same subject(s) Clinical assessment & further investigation at investigator discretion	Study Hold, IMDC Review, VSMB

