9.2.3.2. Assessment of adverse events**9.2.3.2.1. Assessment of intensity**

The intensity of the following solicited AEs will be assessed as described:

Table 24 Intensity scales for solicited symptoms in adults (Amended: 29 January 2014)

Adults		
Adverse Event	Intensity grade	Parameter
Pain at injection site	0	None
	1	Mild: Any pain neither interfering with nor preventing normal every day activities.
	2	Moderate: Painful when limb is moved and interferes with every day activities.
	3	Severe: Significant pain at rest. Prevents normal every day activities.
Redness at injection site		Record greatest surface diameter in mm
Swelling at injection site		Record greatest surface diameter in mm
Fever*		Record temperature in °C/F
Headache	0	Normal
	1	Mild: Headache that is easily tolerated
	2	Moderate: Headache that interferes with normal activity
	3	Severe: Headache that prevents normal activity
Fatigue	0	Normal
	1	Mild: Fatigue that is easily tolerated
	2	Moderate: Fatigue that interferes with normal activity
	3	Severe: Fatigue that prevents normal activity
Respiratory symptoms (cough, blood in sputum, purulent sputum, shortness of breath or difficulties breathing, chestwall pain)	0	No symptoms
	1	Mild: symptoms that are easily tolerated
	2	Moderate: symptoms that interfere with normal activity
	3	Severe: symptoms that prevent normal activity
Malaise	0	Normal
	1	Malaise that is easily tolerated
	2	Malaise that interferes with normal activity
	3	Malaise that prevents normal activity
Myalgia	0	Normal
	1	Myalgia that is easily tolerated
	2	Myalgia that interferes with normal activity
	3	Myalgia that prevents normal activity

*Fever is defined as temperature $\geq 37.5^{\circ}\text{C} / 99.5^{\circ}\text{F}$ for oral, axillary or tympanic route, or $\geq 38.0^{\circ}\text{C} / 100.4^{\circ}\text{F}$ for rectal route. The preferred route for recording temperature in this study will be axillary.

The investigator will assess the maximum intensity that occurred over the duration of the event for all unsolicited AEs (including SAEs) recorded during the study. The assessment will be based on the investigator's clinical judgement.

The intensity should be assigned to one of the following categories:

1 (mild) = An AE which is easily tolerated by the subject, causing minimal discomfort and not interfering with everyday activities.

2 (moderate) = An AE which is sufficiently discomforting to interfere with normal everyday activities.

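### The TVC respiratory AE tables in SAP 11.13 mix two event definitions: early solicited respiratory symptoms in the sub-cohort are left out, while the same symptoms in all other subjects are counted

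*SAP*

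**What the plan says.** SAP 11.13 specifies this measure over the 90 days after vaccination (Day 0 to Day 89): "The proportion of subjects with at least one report of unsolicited AE associated to the respiratory system classified by the MedDRA". It "will be tabulated with exact 95% CI by treatment group, for all subjects in the TVC population". The same tabulation follows for grade 2 or 3, grade 3, related, and the combinations of grade with relatedness. A second table covers Days 0-29: "The proportion of subjects with at least one report of grade 3 unsolicited AE associated to the respiratory system classified by the MedDRA", again for all TVC subjects.

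Protocol 9.1.3 (Table 20) makes respiratory symptoms a solicited general AE. Protocol Table 24 lists what the item covers: "cough, blood in sputum, purulent sputum, shortness of breath or difficulties breathing, chestwall pain". SAP 4.2 restricts solicitation to the sub-cohort, on the day of vaccination and the six days after it, for each dose. The Protocol glossary defines an unsolicited AE as "Any AE reported in addition to those solicited during the clinical study"; a solicited symptom becomes unsolicited only if its onset lies outside the solicited period.

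For subjects outside the sub-cohort, SAP 11.13 says that the listed symptoms, respiratory symptoms among them, "reported for the other subjects were recorded in the Case Report Form (CRF) section on unsolicited symptoms". It then plans three checks on the impact of this: the unsolicited table repeated in the sub-cohort, a table for Days 0 to 7, and a table for Days 7 to 29.

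SAP 11.11 tabulates solicited symptoms in the sub-cohort only, including grade 2 or higher, grade 3 and related events.

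**The concern.** The same cough on Day 3 counts as a respiratory AE in a subject outside the sub-cohort and does not count in a subject inside it. Both stay in the denominator. The omission falls on the subjects who were questioned most actively. The SAP recognises the mixed collection, but all three impact checks remain limited to unsolicited AEs, so none brings the missing events back. SAP 11.10.4 does combine solicited and unsolicited AEs, but only as any local, any general or any AE, and only within the sub-cohort.

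Respiratory AEs are a named safety interest. The holding rules in Protocol 6.4.5.4 turn on their grade and relatedness within 90 days; for example, "An ad hoc IDMC review will be called if 2 or more subjects experience related Grade 2 or higher respiratory AEs" within that window. Those rules do not exclude solicited events. The SAP's 90-day rows by grade and relatedness resemble them but use a narrower event, so a reader who compares the two compares different quantities.

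**Working it through.** The documents give no figure for this effect, so there is none to reproduce.

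**Inputs from the documents**
- Planned enrolment 3506, or 1753 per arm (Protocol 5.1, Table 1).
- Sub-cohort about 450, or about 225 per arm (Protocol 6.2.3, Table 5). Others: 3506 − 450 = 3056.
- Solicited days: 7 after each of two doses = 14 (SAP 4.2).
- Unsolicited AE collection: 30 days after each of two doses = 60 days (Protocol 9.2.1). The table window is 90 days, but routine AE recording covers these 60.

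**Share of the TVC affected**

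f = 450/3506 = 0.128, the same in each arm (225/1753 = 0.128).

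**Upper bound at equal reporting**

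Suppose that every respiratory event is one of the five symptoms with onset in a solicited window, and that no sub-cohort subject has another counted respiratory AE. A true proportion p is then tabulated as p × (1 − f):
- An assumed 5.0% appears as 5.0% × 0.872 = 4.4%.
- An assumed 10% against 5% appears as 8.7% against 4.4%. The difference falls from 5.0 to 4.4 points and the ratio stays at 2.

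**Shortfall over the collection period of the actual table**

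None of the respiratory tables covers Days 0-6 alone. Assume a constant hazard over the 60 days, all events being of the listed kind, and about one event per affected subject:
- Relative shortfall = f × 14/60 = 0.128 × 0.233 = 0.030, or 3.0%.
- An assumed 5.0% appears as 5.0% × 0.970 = 4.85%.

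**If solicitation finds k times as many events**

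Share of all reports left out = f·k·(14/60) / [f·k·(14/60) + f·(46/60) + (1 − f)]. The two fixed terms are 0.128 × 46/60 = 0.098 and 0.872.

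| k | left out | total | share |
|---|---|---|---|
| 2 | 0.060 | 0.060 + 0.098 + 0.872 = 1.030 | 5.8% |
| 3 | 0.090 | 0.090 + 0.098 + 0.872 = 1.060 | 8.5% |

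These are shares of reports. The table counts subjects with at least one event, so a sub-cohort subject with a later respiratory AE is still counted. The values of p and k and the flat hazard are assumptions; the documents give none of them. Clustering of events soon after vaccination would move the shortfall up from 3%.

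**The case against.** The strongest reply accepts the text and disputes the consequence.

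- **The events are reported.** SAP 11.11 gives solicited respiratory symptoms by arm, by grade and by relatedness, with confidence intervals. This stands: nothing is lost from the report. But SAP 11.11 covers only the sub-cohort, and a subject may appear in both tables, so the two cannot simply be added.
- **Only part of the sub-cohort's early respiratory events is missing.** A reader might infer that the sub-cohort contributes no respiratory events on Days 0-6. The documents do not support that. Respiratory AEs outside the five listed symptoms are still unsolicited and counted, as are the listed symptoms with onset after Day 6.
- **Other TVC tables carry respiratory terms.** The general unsolicited tables and the SAE tables are also classified by MedDRA. This stands, but the general unsolicited tables have the same limit, and the SAE tables show only serious events.
- **The holding rules are not affected.** A reader might infer that a hold could be missed. The rules run during enrolment and vaccination, on respiratory AEs without a restriction to unsolicited ones, through in-trial safety review. The SAP tables belong to the analyses after the Month 24 and Month 36 visits (SAP 13.1), and they do not drive the rules.
- **Keeping active and spontaneous collection apart is defensible.** It is, but these tables do not do so: they pool all TVC subjects under a definition that works differently in the two groups.
- **The wording is not fully settled.** The rows by grade and relatedness omit the word unsolicited. The reference back to the same tabulation and the section title most naturally carry it over, but the text should say so.

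**Conclusion.** The point holds as an inconsistency of definition with a modest undercount. Both arms are affected about equally, since the sub-cohort is about 225 per arm. The effect is a lower proportion and a smaller absolute difference; the ratio is roughly unchanged, provided that the timing of events and the yield of solicitation are similar in the two arms. A reader might infer a bias towards one arm, but the design gives no ground for that.

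At equal reporting the bound is 12.8%, and it is reached only if all events fall in the solicited windows. It should not be read as the expected error of the 90-day table. On a flat hazard the figure is about 3%, or about 6% to 8.5% of reports if solicitation finds two to three times as many events, with more if events cluster early. The case for a change rests less on size than on the fact that no TVC respiratory table applies one event definition to all its subjects, and that the data to do so are already collected.

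**What to change.** In SAP 11.13, define the respiratory rows (any, grade 2-3, grade 3, related, and their combinations) as solicited or unsolicited respiratory AEs. State that the composite solicited item for respiratory symptoms maps to the respiratory term list used for these tables, and that it enters with its recorded grade (Protocol Table 24) and the investigator's causality assessment (Protocol 9.2.3.2.2). Count each subject once per row, and show every row overall and split by sub-cohort yes/no.

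The cost is SAP wording, a mapping rule and a data merge. The mapping rule is needed because the tables are built on preferred terms, whereas the solicited item is a single composite that the documents do not say is coded to a term. No new data are required. The reported proportions would rise somewhat. The overall row would mix active and spontaneous collection, which the split makes visible.
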